## 7.2 Safety-Related Data Collection

This section describes eCRF data collection for pre-existing conditions and adverse events. As part of this description, reference is made to severity grading and criteria for EAE reporting; refer to Section 7.3.3 and 7.3.2, respectively, for detailed information on these topics.

The definition of the term adverse event provided in Version 2.0 of the Manual for Expedited Reporting of Adverse Events to DAIDS (DAIDS EAE Manual) will be used in this study. This definition will be applied to all child participants, beginning at the time of first exposure to either study drug. Any untoward medical conditions identified prior to or ongoing at enrollment will be considered pre-existing conditions. Refer to Section 4.8 for more information on defining the effective point of enrollment in the study.

Pre-existing conditions and adverse events will be entered into eCRFs as specified below.

#### **Pre-Existing Conditions**

The following pre-existing conditions will be entered into medical history eCRFs:

- All conditions (i.e., grade 1 or higher) identified during the 28 days prior to or ongoing at study entry
- All prior to study entry significant central nervous system disorders (including seizures and migraines/headaches), mood disorders (such as depression), and significant liver disease resulting in hospitalization or interfering with daily activities
- Any other medical condition (i.e., grade 1 or higher) occurring prior to study entry and deemed clinically significant by the IoR/designee

#### Adverse Events

Adverse events will be entered into the adverse events eCRFs:

- Grade 1 and higher clinical adverse events
- Grade 3 or higher laboratory-only adverse events
- Grade 1 or 2 laboratory adverse events that result in temporary study product hold or permanent discontinuation of study product
- Adverse events that meet criteria for expedited reporting per protocol Section 7.3.2

#### Laboratory Test Results

All protocol-required laboratory test results will be entered into laboratory eCRFs. HIV-1 RNA will be entered into laboratory eCRFs or transferred electronically to the DMC through the LDMS. ARV resistance test results will be transferred electronically to DMC using data submission utilities. Additionally, any non-protocol-required laboratory test results deemed clinically relevant by the investigator may be collected and reported on eCRFs.

# 7.3 Expedited Adverse Event (EAE) Reporting

# 7.3.1 EAE Reporting to DAIDS

Requirements, definitions and methods for expedited reporting of adverse events are outlined in Version 2.0 of the DAIDS EAE Manual, which is available at: https://rsc.niaid.nih.gov/clinical-research-sites/manual-expedited-reporting-adverse-events-daids

The DAIDS Adverse Experience Reporting System (DAERS), an internet-based reporting system, must be used for EAE reporting to DAIDS. In the event of system outages or technical difficulties, EAEs may be submitted using the DAIDS EAE Form. This form is available at: https://rsc.niaid.nih.gov/clinical-research-sites/paper-eae-reporting.

For questions about DAERS, please contact NIAID CRMS Support at: [contact]

Queries may also be sent from within the DAERS application itself.

For questions about expedited reporting, please contact the DAIDS RSC Safety Office at: [contact]

## 7.3.2 EAE Reporting Requirements for this Study

The SAE (serious adverse event) reporting category, as defined in Version 2.0 of the DAIDS EAE Manual, will be used for this study. In addition, the following must also be reported in an expedited manner (i.e., as EAEs), regardless of relationship to study drug:

- Grade 2 or higher ALT or AST with total bilirubin  $\geq 2x$  ULN
- Grade 2 or higher baseline ALT or AST with signs/symptoms of clinical hepatitis
- Grade 3 ALT or AST that persists >2 weeks
- Grade 4 ALT or AST
- Any seizure event

The study agents for which expedited reporting are required are oral cabotegravir (CAB), long-acting injectable cabotegravir (CAB LA), oral rilpivirine (RPV), and long-acting injectable rilpivirine (RPV LA).

Information on adverse events will be included in reports to the US FDA, and other government and regulatory authorities, as applicable.

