# 7.3.4 EAE Reporting Period

The EAE reporting period for this study is the protocol-specified period of follow-up, beginning at the time of study entry and ending on the latest timepoint: Week 72 (Cohort 1), Week 48 (Cohort 2a), 44 (Cohort 2b), or LSFU Week 48.

After the protocol-defined EAE reporting period, unless otherwise noted, only Suspected, Unexpected Serious Adverse Reactions (SUSARs) as defined in Version 2.0 of the DAIDS EAE Manual will be reported to DAIDS if the study staff become aware of the events on a passive basis (from publicly available information).

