#### 8.1.6 Elevations in ALT or AST, Bilirubin

ALT, AST, total bilirubin, and direct bilirubin will be routinely monitored in this study.

In all cases of elevated ALT, AST, and/or elevated bilirubin (total or direct), possible alternative etiology should be assessed, and the underlying illness treated, or the likely causative agent removed. Sites should counsel participants and their parents/guardians about signs and symptoms of hepatotoxicity. Participants should be advised to notify the study site immediately if they develop any concerning signs or symptoms: new or worsening nausea, vomiting, unexplained loss of appetite; yellowing of the skin or eyes; increased weakness or fatigue; pain in the upper abdomen (liver tenderness or hepatomegaly); pale or clay-colored stools; and/or unexplained weight loss.

Elevated bilirubin in the absence elevated ALT or AST should be managed per Section 8.1.1.

ALT or AST results of severity grade 1 or 2 — other than the grade 2 results specified in the first two bullet points below — require no additional action. Study drug should be continued with routine monitoring per the Schedule of Evaluations unless more frequent monitoring is considered clinically indicated in the opinion of the site investigator. If any results of severity Grade 3 or higher are obtained, all four tests (i.e., ALT, AST, total bilirubin, and direct bilirubin) should be repeated as soon as possible and within three business days. Re-evaluation should continue at least weekly until improvement to grade 2 or lower or until stabilized and no longer in need of frequent monitoring, as determined by the site investigator and in consultation with the CMC.

Study drug must be held in the following scenarios (See Section 7.3.2 for EAE reporting requirements):

- Grade 2 ALT or AST with total bilirubin greater than two times the upper limit of normal (>2xULN) and direct bilirubin greater than 35% of total bilirubin. In this case, study drug should be permanently discontinued, and the CMC should be notified.
- Grade 2 or higher ALT or AST with signs or symptoms of clinical hepatitis (e.g., fatigue, nausea, vomiting, right upper quadrant pain, jaundice) or hypersensitivity (e.g., rash, fever, facial edema, eosinophilia, difficulty breathing). In this case, if another cause of the ALT or AST elevation is identified, consideration may be given to resuming study drug with approval from the CMC.

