#### Baseline:

The **baseline value** will be the latest assessment with a non-missing value prior to the first study drug exposure.

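### Section 7.3.2 ties the clinical-hepatitis reporting criterion to 'baseline' ALT/AST, which contradicts Section 8.1.6 and leaves a narrow class of on-treatment events with no required expedited report

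*Protocol*

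**What the plan says.** Section 7.3.2 adopts the SAE category of the DAIDS EAE Manual and adds study-specific events that must be reported in an expedited manner whatever their attribution. Four of the additions concern the liver:

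- "Grade 2 or higher ALT or AST with total bilirubin" at or above 2xULN;
- "Grade 2 or higher baseline ALT or AST with signs/symptoms of clinical hepatitis";
- Grade 3 ALT or AST persisting for more than two weeks;
- Grade 4 ALT or AST.

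Only the second contains the word 'baseline'.

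Section 8.1.6 introduces its own list with "Study drug must be held in the following scenarios (See Section 7.3.2 for EAE reporting requirements". One scenario on that list is "Grade 2 or higher ALT or AST with signs or symptoms of clinical hepatitis", with signs of hypersensitivity as an alternative to hepatitis.

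Three other places fix the timing. Section 9.6 defines the baseline value as the "latest assessment with a non-missing value prior to the first study drug exposure". Section 7.2 applies the adverse event definition "beginning at the time of first exposure to either study drug" and adds: "Any untoward medical conditions identified prior to or ongoing at enrollment will be considered pre-existing conditions". Section 7.3.4 sets the expedited reporting period as "beginning at the time of study entry and ending on the latest timepoint" that applies to the participant.

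**The concern.** The hepatitis items in Sections 7.3.2 and 8.1.6 plainly describe one scenario, and the second section refers to the first for its reporting. Yet the reporting item carries a qualifier that the hold item lacks. A baseline value cannot be an on-treatment signal, so the item as worded does not capture the event that triggers the hold.

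The item is not obviously void either, and that makes the word harder to dismiss. Section 4.1.11 admits children with ALT and AST up to Grade 2 (below 5.0xULN), so a Grade 2 baseline value can exist. A site could apply the item only to children who entered with raised enzymes.

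What is at stake is consistent expedited reporting of a liver signal. Section 1.2.5.1 names drug-induced liver injury as a risk of CAB and describes the otherwise unexplained cases as a mild form without hepatic dysfunction, which is close to the kind of case the literal wording leaves out. Section 13.5 notes that these drugs have not been studied in children under 12, and Section 1.3.1 that the depot cannot be removed.

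**Working it through.** No arithmetic reproduces or refutes the wording. The check sets the sections side by side.

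**Step 1: do the two lists correspond?** The four liver items in Section 7.3.2 and the four hold scenarios in Section 8.1.6 pair off, though not in every detail: raised bilirubin, clinical hepatitis, Grade 3 for more than two weeks, and Grade 4. In the hepatitis pair, 'baseline' stands in Section 7.3.2 and not in Section 8.1.6.

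**Step 2: what does 'baseline' mean?** The general definition in Section 9.6 is pre-exposure. Section 6.12 sets the ECG baseline at screening, and Section 6.10 sets the baseline history at screening and entry. Each of these is before treatment.

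**Step 3: does a pre-exposure value fit a reporting rule?** Under Section 7.2, adverse events start at first exposure and conditions present at enrollment are pre-existing. A raised value at baseline is therefore outside the adverse event definition, and a new on-treatment elevation is not a baseline value. The literal item includes the first and omits the second.

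**Step 4: could 'baseline' mean a change from baseline?** Where the protocol wants that comparison it writes it. The QTc grading in Section 7.3.3 uses an increase over baseline, and Section 8.1.4 speaks of CK raised from baseline. The hepatitis item has no comparative wording.

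**Step 5: which on-treatment events with clinical hepatitis remain reportable?** Consider a child whose own baseline ALT/AST was below Grade 2.

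| On-treatment event with clinical hepatitis | Item in Section 7.3.2 that covers it |
|---|---|
| Meets an SAE criterion | SAE category |
| Grade 2 or higher, total bilirubin at or above 2xULN | Bilirubin item |
| Grade 4 | Grade 4 item |
| Grade 3 for more than two weeks | Persistent Grade 3 item |
| Grade 3 for two weeks or less, bilirubin below 2xULN, non-serious | None |
| Grade 2, bilirubin below 2xULN, non-serious | None |

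Two of the six classes are uncovered.

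**Step 6: what happens to those two classes?** Section 8.1.6 requires a hold. Section 8.4 requires CMC consultation on every temporary hold within 48 hours. Section 7.1.2 places Medical Officers and company medical representatives (or designees) on that committee. Section 7.2 requires eCRF entry of clinical events from Grade 1, laboratory events from Grade 3, and Grade 1 or 2 laboratory events that lead to a hold. The event is therefore known and recorded. Only the report to DAIDS through its expedited system (Section 7.3.1) is not required.

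**The case against.** The strongest reply is that nothing of substance is lost. The literal reading leaves the item almost empty as a rule about adverse events, Section 8.1.6 points to the intended match, and most sites would report as intended. The definition in Section 9.6 belongs to the statistical section, and Section 7 does not define the term. A dropped comparator is as plausible as a stray word. EAE definitions also rest on the DAIDS EAE Manual, which is not at hand.

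Much of this stands. The word is probably a drafting slip, and the text does not show which slip it was, so the remedy has to allow for both. The manual governs what counts as an SAE, but the hepatitis item is one of the study's own additions and should be clear on its face. CMC consultation is guidance on managing the participant and does not replace an expedited report. The monthly check by the DAIDS Medical Officer in Section 9.5.3 looks at expedited events that have been reported, so it would not bring up one that was not.

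Three stronger readings are tempting, and the protocol does not support them:

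- A reader might infer that no new on-treatment Grade 2 elevation with clinical hepatitis is reportable. The bilirubin item and the SAE category still apply.
- A reader might infer that the uncovered cases reach the sponsor side only through monthly safety reports. The mandatory hold and the 48-hour consultation contradict that.
- A reader might infer that safety analyses or interim decisions are affected. The safety outcomes in Section 9.2 and the Safety Guidelines in Section 9.5.2 use grade, seriousness, attribution and discontinuation, and not expedited-reporting status.

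**Conclusion.** The contradiction between Sections 7.3.2 and 8.1.6 is real, and its reach is narrow. Read literally, the protocol does not require an expedited report for a non-serious on-treatment clinical hepatitis with total bilirubin below 2xULN and ALT/AST that is Grade 2, or Grade 3 for two weeks or less. The loss is the formal report, not awareness and not data. No estimand, sample size, error rate or interim rule changes.

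The documents give no rate for this class of event. The nearest figure is in Section 1.2.5: drug-induced liver injury in five participants on oral CAB in Phase I and II, below 1%. If that ceiling carried over to 90 children, which is an assumption, it would mean fewer than 90 x 0.01 = 0.9 such cases. The criterion applies whatever the attribution, however, so hepatitis from other causes would add to the count.

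The conclusion assumes that 'baseline' in Section 7.3.2 has its ordinary pre-exposure meaning in this protocol, and that nothing in the EAE Manual separately requires these events to be reported.

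**What to change.** Reconcile the hepatitis item in Section 7.3.2 with the matching scenario in Section 8.1.6. The simplest way is to delete 'baseline'. If the authors meant a comparison with the child's own baseline, they should write it out, with the size of the increase and the reference value, and explain why the reporting threshold then differs from the hold threshold. The correction can be sent to sites with the next clarification or amendment.

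This changes a reporting rule only and leaves the hold and all participant management as they are. The cost is one deleted word, or one added clause, and a few more expedited reports.

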## 7.3.3 Grading Severity of Events (applies to EAEs and all other adverse events)

The Division of AIDS Table for Grading the Severity of Adult and Pediatric Adverse Events (DAIDS AE Grading Table), Corrected Version 2.1, dated July 2017, will be used in this study,

except where otherwise noted below. This table is available on the RSC website at https://rsc.niaid.nih.gov/clinical-research-sites/daids-adverse-event-grading-tables.

QTc Intervals: QTc intervals must be calculated using the Fridericia QT correction formula (provided in the IMPAACT 2036 MOP), with the below specified grading:

	Grade 1	Grade 2	Grade 3	Grade 4
QTc Prolongation Interval	QTc ≥ 460msec, but < 480msec	QTc ≥ 480msec, but < 500msec	$QTc \ge 500 \text{msec}$ $QTc > 60 \text{ msec}$	Life-threatening consequences (e.g., Torsades de pointes, other
			greater than baseline AND QTc ≥480 ms	serious ventricular dysrhythmias)

Creatinine and eGFR: Grading of creatinine and eGFR should be based on absolute value only (note the Bedside Schwartz formula provided in the IMPAACT 2036 MOP must be used for calculating eGFR), with the below specified grading:

	Grade 1	Grade 2	Grade 3	Grade 4
Creatinine, High	1.1 to 1.3 x ULN	> 1.3 to 1.8 x ULN	> 1.8 to < 3.5 x ULN	≥ 3.5 x ULN
eGFR, Low	NA	< 90 to 60 ml/min/1.73 m 	< 60 to 30 ml/min/1.73 m 	< 30 ml/min/1.73 m 

Fever: When temperatures are collected, clinical discretion should be used to determine if an axillary or non-axillary temperature is most appropriate, with the below specified grading used for participant safety management:

	Grade 1	Grade 2	Grade 3	Grade 4
Fever (axillary temperature)	37.4 to <38.0°C	38.0 to <38.7°C	38.7 to <39.4°C	≥39.4°C
Fever (non-axillary temperature)	38.0 to < 38.6°C or 100.4 to < 101.5°F	$\geq 38.6 \text{ to}$ $< 39.3^{\circ}\text{C}$ or $\geq 101.5 \text{ to}$ $< 102.7^{\circ}\text{F}$	$\geq$ 39.3 to < 40.0°C or $\geq$ 102.7 to < 104.0°F	≥ 40.0°C or ≥ 104.0°F

# 7.3.4 EAE Reporting Period

The EAE reporting period for this study is the protocol-specified period of follow-up, beginning at the time of study entry and ending on the latest timepoint: Week 72 (Cohort 1), Week 48 (Cohort 2a), 44 (Cohort 2b), or LSFU Week 48.

After the protocol-defined EAE reporting period, unless otherwise noted, only Suspected, Unexpected Serious Adverse Reactions (SUSARs) as defined in Version 2.0 of the DAIDS EAE Manual will be reported to DAIDS if the study staff become aware of the events on a passive basis (from publicly available information).

### 8 PARTICIPANT MANAGEMENT

## 8.1 Management of Adverse Events

All adverse events identified in this study will be source documented in participant research records, consistent with the policies and procedures referenced in Section 11.2. Among other details, source documentation will include the severity of each event (graded as described in Section 7.3.3) and its relationship to study drug, assessed by the site clinician according to the following categories and definitions:

**Related** There is a reasonable possibility that the adverse event may be related to the study

agents: oral cabotegravir (CAB), long-acting injectable cabotegravir (CAB LA), and

oral rilpivirine (RPV), and long-acting injectable rilpivirine (RPV LA)

**Not related** There is not a reasonable possibility that the adverse event may be related to the

study agents: oral cabotegravir (CAB), long-acting injectable cabotegravir (CAB LA), and oral rilpivirine (RPV), and long-acting injectable rilpivirine (RPV LA)

Further standardized guidance on determining whether there is a reasonable possibility of a relationship is available in the DAIDS EAE Manual, referenced in Section 7.3.1 above.

Adverse events identified in enrolled participants will be managed based on their severity and assessed relationship to study product, as described in greater detail below.

Individual dose adjustments or reductions of study products for management of toxicity-related adverse events are not allowed. In the event of a temporary study product hold or a permanent discontinuation of study product, both study products will always be held (or discontinued). For additional considerations regarding participants resuming (non-study provided) cART, see Section 8.4 regarding temporary product holds, and Section 8.5 regarding permanent discontinuation of study product.

All adverse events must be followed to resolution (return to baseline) or stabilization (absence of further deterioration), with the frequency of repeat evaluations determined by the clinical significance of each event. Additional evaluations beyond those listed in the Schedules of Evaluations (see Appendix I) may be performed at the discretion of the site investigator to determine the etiology of a given event and/or further assess its severity or relationship to study product. Clinical management of all adverse events should be provided consistent with the best medical judgment of the site investigator and local clinical practice standards.

Participants with Grade 3 or higher adverse events at their last regularly scheduled study visit should remain on study for up to 28 days or until resolution or stabilization, whichever is sooner. The frequency of any additional visits is determined by the site investigator. If this is not possible, the site investigator should actively facilitate referral to local non-study sources of appropriate medical care and treatment.

Unless otherwise specified, when management of an adverse event requires consultation with the CMC, the CMC should be contacted as soon as possible and within two business days of site awareness of the event.

# 8.1.1 General Management of Adverse Events

Sections 8.1.2—8.3 provide detailed participant and study product management on specified adverse events including specified abnormal laboratory test result values. If an observed adverse event or abnormal laboratory test result value is not listed in those sections below, the guidance in this section (General Management of Adverse Events) should be followed.

In general, the IoR or designee has the discretion to temporarily hold study product at any time if they feel that continued product use would be harmful to the participant or interfere with treatment deemed clinically necessary. See Sections 8.4 and 8.5 below.

- Grade 1 or Grade 2, regardless of relationship to study drug: Continue study product and manage participant according to standard of care practice at the site.
- **Grade 3 assessed as not related:** Continue study product and re-evaluate participant at least weekly until improvement to Grade 2 or lower. If improvement to Grade 2 or lower cannot be documented in 2 weeks, consult the CMC.
- **Grade 3 assessed as related:** Temporarily hold study product use, notify the CMC, and reevaluate the participant at least weekly until improvement to Grade 2 or lower. If within 2 weeks the adverse event has improved to Grade 2 or lower, study product may be resumed. Consult the CMC if improvement to Grade 2 or lower cannot be documented within 2 weeks
  - o If study product use is resumed and the same Grade 3 adverse event deemed related to study product, recurs at any time, the IoR/designee must temporarily hold study product and consult the CMC for further guidance on continuing the temporary hold or progressing to permanent discontinuation of the study product.
- **Grade 4 regardless of relationship to study drug:** Temporarily hold study product, re-evaluate the participant as soon as possible or within 2 business days, and consult the CMC. Continue the temporary product hold until a recommendation is obtained from the CMC.

